## C. Patients and community engagement

- C.1. Patient empowerment: sessions where "expert hypertensive patients" will provide support and peer-education to other patients in need, such as those newly diagnosed or non-adherent to treatment or with uncontrolled hypertension, under the supervision of a social worker.
- C.2. Community engagement: A Community Hypertension Outreach Group (CHOG) will be set up, composed by three voluntary community health workers who will be trained and certified. The CHOG will be created in partnership with the patients' association, which is a very dynamic organization already present in the Commune and interested in engaging in the project. The CHOG will conduct screening activities with measurements of BP in selected public areas of the commune on a weekly rotation basis, for all adults without BP readings in the previous year and referral of those with a positive screening to the nearest health facility for diagnosis confirmation. The CHOG will provide health education with emphasis on healthy lifestyles (tobacco cessation, physical activity and healthy diet). It will contribute to increase community awareness on the importance of hypertension control and on cardiovascular risk detection and prevention. Existing local communication channels such as the community radio and the local newspaper will also be used.

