**Table 3. Performance indicators at health facility level.**

Indicator	Numerator	Denominator	Data Source	Breakdown	Frequency of collection
1. Number of hypertensive patients enrolled in the Cardiovascular	Number of hypertensive patients enrolled in the CVRP	NA	Billing and electronic clinical records	Cardiovascular risk level (low, medium, high), grade of hypertension (I, II, III)	Monthly

Risk Program (CVRP)				II, resistant), sex, age, pharmacological treatment (yes, no), co-morbidities, complications, health care setting	
2. Prevalence of diagnosed hypertension in Metrosalud's catchment area	Number of hypertensive patients enrolled in the CVRP	Total population for whom Metrosalud is responsible in the studied Commune	For the numerator: Billing and electronic clinical records  For the denominator : Database of the Subsidized Regime and non-insured assigned population	Cardiovascular risk level (low, medium, high), grade of hypertension (I, II, resistant), sex, age, pharmacological treatment (yes, no), co-morbidities, complications, health care setting	Quarterly
3. Ratio of prevalence of diagnosed hypertension to the expected prevalence of hypertension in Metrosalud's catchment area	Prevalence of diagnosed hypertension in Metrosalud's catchment area	Expected prevalence of hypertension in the population for whom Metrosalud is responsible in the catchment area	For the numerator: Billing and electronic clinical records  For the denominator : Survey "Gaps in hypertension care and control in two Communes".	Sex, age, health care setting	Quarterly
4. New hypertensive	Total number of new	NA	Billing and electronic	Cardiovascular risk level (low,	Monthly

patients enrolled in the CVRP	hypertensive patients enrolled in the CVRP during a month		clinical records	medium, high), grade of hypertension (I, II, resistant), sex, age, pharmacological treatment (yes, no), co-morbidities, complications, health care setting	
5. Cardiovascular risk assessment	Hypertensive patients with a recorded cardiovascular assessment in the last 1 year	Number of hypertensive patients enrolled in the CVRP	Billing and electronic clinical records	Cardiovascular risk level (low, medium, high), grade of hypertension (I, II, resistant), sex, age, pharmacological treatment (yes, no), co-morbidities, complications, health care setting	Annual

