6. High calculated cardiovascular risk	Hypertensive patients with calculated cardiovascular disease risk $\geq 20\%$ in 10 years and systolic blood pressure (BP) $\geq 140/90$ mm Hg at last BP measurement during the last year.	Number of hypertensive patients enrolled in the CVRP	Billing and electronic clinical records	Pharmacological treatment (yes, no), sex, age	Biannual
7. Prevalence of controlled	Hypertensive patients with documented	Number of hypertensive patients	Billing and electronic clinical	Pharmacological treatment (yes,	Biannual

hypertension	systolic BP <140 mm Hg and diastolic BP <90 mm Hg in at the most recent BP measurement during the last year.	enrolled in the CVRP	records	no), sex, age	
8. Prevalence of controlled hypertension 6 months after enrolment in the CVRP	Hypertensive patients who started treatment 6 months before the reporting trimester and have systolic BP <140 mm Hg and diastolic BP <90 mm Hg at follow-up visit during the reporting trimester	Number of hypertensive patients enrolled in the CVRP who started treatment 6 months before the reporting trimester	Electronic clinical records	Sex, age, pharmacological treatment (yes, no), non-pharmacological treatment (yes, no)	Quarterly
9. Uncontrolled hypertension in patients with cardiovascular disease, renal disease or diabetes	Hypertensive patients diagnosed $\geq 6$ months before the start of the reporting period, and cardiovascular disease, renal disease, or diabetes mellitus, who had systolic BP $\geq 140$ mm Hg or diastolic BP $\geq 90$ mm Hg at the most recent BP measurement during the last	Number of hypertensive patients enrolled in the CVRP $\geq 6$ months before the start of the reporting period	Electronic clinical records	Pharmacological treatment (yes, no), sex, age	Quarterly

	year				
10. Uncontrolled hypertension 2	Hypertensive patients diagnosed $\geq 6$ months before the start of the reporting period who had systolic BP $\geq 160$ mm Hg or diastolic BP $\geq 100$ mm Hg at the most recent BP measurement during the last year	Number of hypertensive patients enrolled in the CVRP $\geq 6$ months before the start of the reporting period	Electronic clinical records	Pharmacological treatment (yes, no), sex, age	Quarterly

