11. Resistant hypertension	Hypertensive patients diagnosed $\geq 6$ months before the start of the reporting period and who are treated with three or more antihypertensive drugs, who had systolic BP $\geq 160$ mm Hg or diastolic BP $\geq 100$ mm Hg at the most recent BP measurement during the last year	Number of hypertensive patients enrolled in the CVRP $\geq 6$ months before the start of the reporting period	Electronic clinical records	Sex, age	Quarterly
12. Six-monthly control of blood pressure among people started on pharmacological treatment for	Number of patients started on pharmacological treatment of hypertension during the	Number of patients started on pharmacological treatment of hypertension	Electronic clinical records	Sex, age	Quarterly

hypertension	quarter that ended 6 months before, with controlled blood pressure (SBP<140 and DBP<90) at the last clinical visit in the most recent quarter (just before the reporting quarter)	during the quarter that ended 6 months before			
--------------	---	---	--	--	--

The indicators for measuring the process implementation of different components of the intervention are listed in Table 4.

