## 8. DATA MANAGEMENT AND ARCHIVING

### 8.1 Data Management

Data will be collected as described in section 4. Databases will be electronically encrypted, and a single study code will be assigned to each participant and they will be password-protected, with a password known only to the research team. The list of participant names and their assigned study codes will be stored in a separate database with restricted access to the study investigators that did the process of identification. Data will be analysed as described in section 4. The obtained individual information will be known only by the research team, where information access levels will be established, in particular for personal identification data. For the endline survey, questionnaires will be filled in by using tablets, and the information will be consolidated through an electronic platform provided by a professional statistics enterprise. The access to each electronic questionnaire is restricted to specifically authorized surveyor. The software of the electronic platform will allow to record in real-time every applied single questionnaire, obtaining reliable databases. Only aggregate data will be extracted from the billing and electronic clinical records of Metrosalud and from the databases of the subsidized regimen and of the non-insured poor population. Qualitative information will be transcribed *verbatim* by trained personnel. Transcripts and data will be stored in Nvivo v.10 and analysed as described in section 4.3.2. Anonymity of participants will be maintained, a code will be assigned to every participant and transcripts will be anonymous for transcribers. Data protection and confidentiality will be responsibility of the PI and the responsible for qualitative analysis.

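### Six-month BP control among treatment starters (Table 3, indicators 8 and 12) has no breakdown by starting severity, so screening in one commune only could shift the crude comparison, in either direction, with no difference in care

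*Combined protocol and SAP*

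**What the plan says.** Section 4.3.1 gives Table 3 two purposes: to monitor implementation, and to measure the intervention's results and effects at health service level. Its indicators are measured in both communes at baseline, at intervals during implementation, and at endline.

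Indicator 8 takes as its numerator "Hypertensive patients who started treatment 6 months before the reporting trimester and have systolic BP <140 mm Hg and diastolic BP <90 mm Hg" at a follow-up visit in the reporting trimester. Indicator 12 counts people started on drug treatment "with controlled blood pressure (SBP<140 and DBP<90) at the last clinical visit in the most recent quarter". Both denominators are the people who started treatment. Indicator 8 is broken down by sex, age, drug treatment (yes/no) and non-drug treatment (yes/no). Indicator 12 is broken down by sex and age only.

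Indicators 1, 2, 4 and 5 of the same table carry a fuller breakdown, by cardiovascular risk level and then "grade of hypertension (I, II, resistant), sex, age, pharmacological treatment (yes, no), co-morbidities, complications, health care setting".

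Active screening belongs to the intervention. Section 4.2.1 A.1 has adults aged 35 or older at any health service asked about a recent BP measurement and referred if they have had none. Under C.2, "The CHOG will conduct screening activities with measurements of BP in selected public areas of the commune on a weekly rotation basis". Section 4.2 gives the control commune standard care.

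The logistic regression in section 4.3.1 is described for the population-level gaps of Table 1. No case-mix adjustment is described for Table 3. Section 8.1 states: "Only aggregate data will be extracted from the billing and electronic clinical records of Metrosalud".

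**The concern.** An outcome proportion in a group that the intervention helps to select mixes two things: how well patients are treated, and who they are. People who start close to 140/90 mm Hg can be expected to fall below it more often than people who start well above it. If screening changes the share of such people among new starters in Santa Cruz and not in Doce de Octubre, indicators 8 and 12 move even when each grade is treated equally well in both communes.

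Subtracting baseline does not remove this, because the mix would change mainly where screening is introduced. What is at stake is the reading of two facility-level results that bear on secondary objective 1, the quality of hypertension care in the public primary services of Santa Cruz.

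**Working it through.** **Inputs.** The documents state no expected value for indicators 8 or 12, no control rate by grade, and no severity mix of new starters, so there is no plan figure to reproduce. The survey's 280 hypertensive individuals (section 4.1.2) plays no part here. All rates below are assumptions.

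**Formula.** Let *m* be the share of starters in grade I, and *c1* and *c2* the six-month control in grade I and grade II, held equal in the two communes so that care does not differ.

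Crude control = *m* × *c1* + (1 − *m*) × *c2*

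Difference between communes = (difference in *m*) × (*c1* − *c2*)

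**Central case.** *c1* = 70%, *c2* = 45%, grade I share 50% in the control commune.

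- Control commune: 0.50 × 0.70 + 0.50 × 0.45 = 0.575.
- Intervention commune, grade I share 70%: 0.70 × 0.70 + 0.30 × 0.45 = 0.625. Difference +5.0 points.
- Intervention commune, grade I share 30%: 0.30 × 0.70 + 0.70 × 0.45 = 0.525. Difference −5.0 points.

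**Range**, in percentage points. The sign follows the direction of the shift in grade I share.

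| Control in grade I / grade II | 10-point shift | 20-point shift | 30-point shift |
|---|---|---|---|
| 65% / 50% | 1.5 | 3.0 | 4.5 |
| 70% / 45% | 2.5 | 5.0 | 7.5 |
| 75% / 40% | 3.5 | 7.0 | 10.5 |

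**Effect of standardising.** Weighting both communes to the same 50/50 mix gives 0.575 in each, a difference of 0. This holds by construction, since care was set equal. It shows that the adjustment targets the right quantity, not that the bias is present.

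**Attendance.** The denominators are all starters, so a starter without a visit in the window counts as not controlled. Read the rates above as applying to attenders, and assume 85% attendance in the control commune: 0.85 × 0.575 = 0.489. With the +5.0-point mix, the intervention commune shows the same figure if its attendance is 0.489 / 0.625 = 78%. A fall of about 7 points in attendance therefore cancels the central case. This is a separate mechanism from case mix, and a breakdown by grade does not remove it.

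**What existing indicators offer.** Indicator 4 reports new enrolees in the cardiovascular risk programme by grade, so a change in entry mix could be seen. It is not cross-classified with six-month control, so it could reveal a shift but not correct for it. The drug-treatment split in indicator 8 is at most a rough proxy for severity and is itself a care decision.

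**The case against.** The strongest objection is that the direction is not known. A reader might infer that the indicators must favour the intervention commune. The documents do not support that.

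- The Healthy Hearts service uses serial self-measured BP to exclude white-coat hypertension (section 4.2.1 A.2). This can remove people with transient or borderline readings, who would easily count as controlled, and so make the remaining starters more severe.
- Screening aims at people with no reading in the previous year. Section 1.2 reports that 45% of unaware hypertensives had no contact with formal health services in the last year. Nothing shows that these people are milder. Table 2 says that mild or absent symptoms shape care seeking, but symptoms are not BP level.
- Lower six-month attendance could offset a milder mix, as computed above.

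This stands. It changes the claim from a bias of known sign to one of unknown sign. It does not make the crude comparison interpretable.

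A second objection is that little rests on these indicators. The main outcomes are the survey gaps of Table 1. No test or decision rule is attached to indicators 8 and 12, and indicators 28 to 31 (correct prescription, recommended drugs, advice given) measure treatment quality more directly. This also stands and limits the weight of the point.

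A third is that section 8.1 does not bar a second extraction, and section 4.2.2.1.2 lists BP figures among the data to be taken from the records. A reader might infer that severity could never be recovered. That holds only for aggregates already extracted; a new query could still supply it. Specifying the stratum beforehand avoids that query.

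Finally, adjustment may be incomplete. The grade field is not defined as grade at start of treatment, and training in BP measurement (B.1) could change recorded grade in one commune.

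**Conclusion.** The point holds in a limited form. As written, the crude between-commune comparison of indicators 8 and 12 is open to case-mix change caused by the intervention's own screening, and Table 3 provides no means of separating that from better care. Under the assumed rates the artefact is about 1.5 to 10.5 points in absolute size, with 5.0 in the central case, and it may go either way. This rests on two things that the documents do not establish: that screening shifts the grade mix of starters by 10 to 30 points, and that six-month control differs between grades by 15 to 35 points.

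The documents do not support reading this as a threat to the trial's main result: the difference-in-difference analysis of the survey gaps does not use these indicators. It is a cheap improvement to two facility-level measures.

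**What to change.** Before extraction, baseline included, add grade of hypertension at start of treatment to the breakdown of indicators 8 and 12 in both communes. State which recorded BP defines the grade, since the existing categories (I, II, resistant) are not tied to treatment start. Report commune comparisons within grade, or directly standardised to one common baseline grade mix fixed in advance, beside the crude figures. Show the share of starters with no visit in the window as well, so that attendance is not mistaken for control.

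Route of detection cannot serve as a stratum between communes, because Healthy Hearts and the community outreach group are intervention components with no counterpart in the control commune. It may be reported descriptively within Santa Cruz, if the records already hold it; otherwise it may need linkage to separate registers.

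The cost is one field of a kind that Table 3 already draws from the records, plus the count of starters with no visit. The downside is small quarterly cells by grade, which may need half-yearly pooling.

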**Table 4. Quantitative indicators for measuring process implementation.**

**A. Indicators related with the performance of the “Healthy Hearts” service in the quality improvement of BP screening and hypertension diagnosis**

Indicator	Numerator	Denominator	Data Source	Breakdown	Frequency of collection
13. Effective availability of the Healthy Hearts service	Number of effective opening hours of the Healthy Hearts service in a week	Number of programmed opening hours of the Healthy Hearts service per week	Register of opening hours of the Healthy Hearts service. Staff shift chart (initial and final)	Days, time	Weekly
14. Effective referral to the Healthy Hearts service and BP screening	Number of people without BP measurement in the last 1 year and referred for BP screening	Total number of people without BP measurement in the last 1 year referred for BP measurement to the Healthy	Numerator: register of people without BP measurement in the last 1 year who receive BP measurement at	Referring service, age, sex, health insurance scheme, patient or caretaker, result of BP measurement	Monthly

	measurement that reach and receive BP screening at the Healthy Hearts service	Hearts service	the Healthy Hearts service Denominator: ticket stubs for referral to Healthy hearts service	(high BP or not)	
15. Referral for serial BP measurement to the Healthy Hearts service	Number of patients not previously enrolled in the CVRP, with high BP at doctor or nurse consultation, referred for serial BP measurement to the Healthy Hearts service during the reporting month	Total number of patients not previously enrolled to the CVRP with high BP at doctors or nurses consultation during the reporting month	Electronic clinical record (referral to Healthy Hearts services)	Type of consultation, age, sex, chronic patient (yes, no)	Monthly
16. Realization of serial BP measurements at Healthy hearts service	Number of individuals with high BP detected by BP screening at the Healthy Hearts service who receive serial BP measurements	Total number of individuals with high BP detected by BP screening at the Healthy Hearts service	Electronic clinical records. Register of individuals who receive serial BP measurements at the Healthy Hearts service	Referring service (Healthy Hearts service, clinical services or A Community Hypertension Outreach Group (CHOG)) Age, sex, patient or caretaker, chronic patient (yes, no)	Monthly
17. Result of serial BP measurement	Number of patients with average systolic BP $\geq 140$ mm Hg or diastolic BP $\geq 90$ mm Hg at	Number of individuals receiving serial BP measurements	Register of serial BP measurements at Healthy Hearts service	Referral service (Healthy Hearts service, clinical services or CHOG)	Monthly

	serial BP measurement			Age, sex, patient or caretaker, chronic patient (yes, no) Cardiovascular risk level.	
18. Indication of serial self-measured BP monitoring	Number of individuals with indication of serial self-measured BP monitoring	Number of individuals with average systolic BP $\geq 140$ mm Hg or diastolic BP $\geq 90$ mm Hg as result of a serial BP measurement	Register of serial self-measured BP monitoring at Healthy Hearts service	Age, sex, patient or caretaker, health insurance scheme	Monthly
19. Realization of serial self-measured BP monitoring	Number of patients with serial self-measured BP monitoring	Number of patients with indication of serial self-measured BP monitoring	Register of serial self-measured BP monitoring at Healthy Hearts services	Age, sex, patient or caretaker, health insurance scheme	Monthly
20. Result of serial self-measured BP monitoring	Number of patients with average systolic BP $\geq 140$ mm Hg or diastolic BP $\geq 90$ mm Hg as result of a serial self-measured BP monitoring	Number of patients with serial self-measured BP monitoring	Register of serial self-measured BP monitoring at Healthy Hearts services	Age, sex, patient or caretaker,	Monthly

**B. Indicators related with the clinical management of the cardiovascular risk program for hypertensive patients**

Indicator	Numerator	Denominator	Data Source	Breakdown	Frequency of collection
21. Realisation of BP measurements by medical and	Number of interviewed individuals referring they	Total number of exit-interviews	Annex 4 (Exit-interview on adherence of clinical staff to	Age, sex, patient or caretaker, chronic patient (yes, no), kind of	Every 2 months

nursing staff	had BP measurement		cardiovascular duties	consultation / service	
22. Missed hypertension-related appointment	Number of patients who missed their last hypertension-related appointment during the reporting week	Patients with scheduled hypertension follow-up visit during the reporting week	Electronic records of Metrosalud	Sex, age, pharmacological treatment (yes, no)	Weekly
23. Management of missed hypertension-related appointment 1	Patients who missed a hypertension-related appointment in the reporting week that were contacted and provided with a new appointment	Patients who missed a hypertension-related appointment in the reporting week	Register of missed hypertension-related appointment in the Healthy Hearts service	Sex, age, pharmacological treatment (yes, no)	Weekly
24. Management of missed hypertension-related appointment 2	Patients who missed a hypertension-related appointment that presented at the new appointment provided by health services	Patients who missed a hypertension-related appointment that were contacted and provided with a new appointment	-Register of missed hypertension-related appointment at CVRP - clinical records	Kind of contact to provide the new appointment (by phone or through community leaders)	Weekly

25. Effective meetings of CVRT for programme follow-up	Number of meetings realized	Number of programmed meetings	List of participants. Minutes of the meetings.	NA	Quarterly
26. Audits of clinical records of patients enrolled in the CVRP	Number of audits of clinical records realized	Number of programmed audits to clinical records	Audit format: Audit of clinical records of hypertension CVRT audit plan of the	NA	Every 2 months
27. Collective feedback to health professionals of the CVRP	Number of feedback meetings involving health professionals of the CVRP	Number of programmed meetings	List of participants. Minutes of the meetings. CVRT meetings schedule	NA	Every 2 months
28. Correct prescription of pharmacological treatment	Number of patients who received a correct prescription of pharmacological treatment according to clinical condition and defined algorithm	Total number of audited clinical records	Report of audit of clinical records	Age, sex, health facility, cardiovascular risk level	Every 2 months
29. Use of recommended antihypertensive drugs	Number of patients who received prescription of antihypertensive drugs included in the standardized	Sample of hypertensive patients receiving pharmacological treatment	Electronic clinical records	Name of anti-hypertensive, age, sex, health facility, cardiovascular risk level, time of diagnosis	Quarterly

	algorithm				
30. Pharmacological advice by the medical doctor during consultation	Number of interviewed hypertensive patients who referred they received pharmacological advice by the medical doctor	Total number of interviewed patients during the audit	Annex 4 (Exit interview on adherence of clinical staff to cardiovascular duties)	Age, sex, health facility, cardiovascular risk level	Every 2 months
31. Percentage of hypertensive patients who received prescription of non-pharmacological treatment	Number of interviewed who refer they received prescription of non-pharmacological treatment by the doctor	Total number of exit interviews	Annex 4 (Exit-interview on adherence of clinical staff to cardiovascular duties)	Age, sex, health facility, cardiovascular risk level	Every 2 months

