The study showed a prevalence of hypertension of 43.4%. Among the total hypertensive individuals, 36.7% were unaware of their diagnosis. Of the aware hypertensives, 93% had been prescribed pharmacological treatment, but 7% of those who had been prescribed treatment were not taking any medication and only 65% of those taking treatment referred treatment compliance. Moreover, 15% of the aware hypertensives did not have any follow-up consultation during the previous year. Among the aware hypertensives, 41% had uncontrolled hypertension. Nineteen percent of aware hypertensives and 45% of unaware hypertensives did not have contact with formal health services in the last year, mainly because they did not feel the need. On the other hand, 55% of unaware hypertensives accessed to health care in the previous year but health services failed to diagnose them.

Studies specifically aimed at reducing the gaps and barriers to hypertension care and control at population level in the country are needed.

The results of the baseline study, the possible determinants of the identified gaps and potential solutions were discussed in a workshop held in Medellin-city, with the participation of ITM staff, the University of Antioquia and Metrosalud. A summary of the identified potential determinants of the main gaps, mainly related to disease detection and quality of care, is presented in Table 2.

**Table 2. Potential determinants at health provider, population and health system level of the main health coverage gaps for hypertension care and control in the Santa Cruz Commune**

Hypertension Coverage Gap / Source of barriers	Health Provision	Population	Health Services
Diagnosis Gap	
 
- No measurement of blood pressure during health care contacts
 
- High blood pressure is detected but confirmation of diagnosis fails due to lack of continuity of care
 
	
 
- Low risk perception of hypertension
 
- Mild or no symptoms determine health seeking
 
	
 
- Passive and fragmented health services
 
- Limited opening hours of services for hypertension detection
 

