#### A.3. Improvement of clinical management of patients with hypertension

A.3.1. Creation of the cardiovascular risk team (CVRT), which will include the head and one leading medical doctor of the hospital unit, and the coordinating doctors of the two health centres. The CVRT will be responsible of supervising good clinical management of hypertension. It will conduct audits of clinical records, periodically selecting a representative sample of clinical records of hypertensive patients and using a structured questionnaire – see annex 5 - to evaluate if the clinical records fulfil the requirements of a complete cardiovascular risk assessment interview and physical examination, doctors' adherence to the hypertension management guideline and some parameters to assess the quality of the provided health care. The CVRT will also provide regular active feedback and support to health professionals involved in the CVRP. It will also supervise the Healthy Hearts service.

A.3.2. Guideline-based standardized diagnostic and treatment protocols: before the start of the intervention, the diagnostic algorithm will be standardized and a simplified and implementable drug treatment algorithm will be defined, based on the national clinical guidelines and in agreement with the general direction of Metrosalud, the direction of the health area and the clinical staff. A core set of antihypertensive medications will be identified and primary and secondary options will be defined for each of the major pharmacologic classes of antihypertensive drugs (diuretics, angiotensin-converting enzyme inhibitors/angiotensin II receptor blockers, calcium channel blockers and Beta-blockers).

A.4. Availability of antihypertensive medications: the availability of the defined core set of antihypertensive medications will be assured through the central store of Metrosalud. Any (un-)availability of antihypertensive medications will be communicated to clinicians at the beginning of each week and *ad hoc* in case of intervening stock-out, in order to timely inform them on possible alternative prescription.

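### Indicator 28 divides correct drug prescriptions by all audited records, so if some patients have no drug indicated and are not credited, it cannot reach 100% and shifts with case mix

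*Combined protocol and SAP*

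**What the plan says.** Indicator 28 (section 4.3.1, Table 4B) measures correct drug prescribing. Its numerator is "Number of patients who received a correct prescription of pharmacological treatment according to clinical condition and defined algorithm". Its denominator is "Total number of audited clinical records".

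The audited records come from the cardiovascular risk team, which works by "periodically selecting a representative sample of clinical records of hypertensive patients" (section 4.2.1, A.3.1). Indicator 26 places the audit within the CVRP: "Audits of clinical records of patients enrolled in the CVRP". Neither place restricts the audit to patients on drugs, or to patients who should be on them.

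The plan allows for CVRP patients without drug treatment. In Table 3, indicator 8 covers patients who have started treatment, yet its breakdown is "Sex, age, pharmacological treatment (yes, no), non-pharmacological treatment (yes, no". Indicators 1, 2, 4 and 5 are also split by whether the patient has drug treatment.

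The next row of Table 4B, indicator 29, has a narrower denominator: "Sample of hypertensive patients receiving pharmacological" treatment.

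The standard against which indicator 28 is judged does not exist yet. Under A.3.2, "a simplified and implementable drug treatment algorithm will be defined" before the intervention starts.

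**The concern.** The numerator and denominator cover different groups. To enter the numerator, a patient must have received a drug prescription. To enter the denominator, a patient need only have been audited. Read literally, a patient whom the algorithm leaves without a drug, and who is correctly given none, has no route into the numerator and is not excluded from the denominator. That record lowers the score exactly as a prescribing error would.

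Two consequences follow if such patients exist. Perfect adherence would score below 100%. The indicator would also change when the mix of audited patients changes, over time or between facilities, with no change in prescribing. The second matters more in this trial, because screening and referral are meant to bring new patients into the programme over 24 months, so the mix may not stay constant.

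What is at stake is the process evaluation, which is a stated secondary objective. Section 4.3.2 also plans to contrast implementation data with outcomes. Among the listed indicators, 28 is the only one that judges whether the prescription was right for the patient's clinical condition.

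**Working it through.** The plan gives no target, expected value or sample size for indicator 28, so there is no figure to reproduce. The check is ratio algebra.

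**Definitions**
- q = share of audited records for which the algorithm indicates no drug. The documents do not give it.
- a = share correctly prescribed among records with a drug indicated.
- All q records are taken to be correctly left without a drug.

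**Three ways to score the indicator**
1. As written, with no-drug records not credited: a(1 − q). The maximum, at a = 1, is 1 − q.
2. Denominator limited to records with a drug indicated: a(1 − q)/(1 − q) = a.
3. All records kept, with correct non-prescription credited: a(1 − q) + q.

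**Anchor for q.** Section 1.2 reports for 2016: "Of the aware hypertensives, 93% had been prescribed pharmacological treatment". So 100% − 93% = 7% had none prescribed. (The same paragraph gives another 7%, for people prescribed drugs but not taking them; that figure is not used here.) The survey does not say how many of the unprescribed 7% had no drug indicated.
- If all of them should have had a drug, q = 0 and the ceiling is 1 − 0 = 100%.
- If none of them should have, q = 0.07 and the ceiling is 1 − 0.07 = 93%.

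**Results** (q = 3.5% is simply the midpoint)

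| q | a | As written | Restricted denominator | Non-prescription credited |
|---|---|---|---|---|
| 0 | 100% | 100% | 100% | 100% |
| 3.5% | 100% | 96.5% | 100% | 100% |
| 7% | 100% | 93% | 100% | 100% |
| 0 | 90% | 90% | 90% | 90% |
| 7% | 90% | 83.7% | 90% | 90.7% |

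**Case-mix effect.** Hold prescribing quality at a = 90% (an illustrative value) and let q go from 0 to 7%. The indicator as written falls from 90% to 0.90 × 0.93 = 83.7%, or 6.3 points, although prescribing has not changed. The restricted denominator stays at 90%. Crediting non-prescription gives 0.837 + 0.07 = 90.7%, so it removes the ceiling but still moves slightly with q.

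**The case against.** The strongest objection is that the premise is unproven. The algorithm is still to be defined, and the documents do not say whether it will leave anyone without a drug. Table 3 shows that patients without drug treatment are expected in the programme, not that they are correctly without it. This stands: a reader might infer that full adherence can never score 100%, but that holds only if q is above zero.

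Second, an auditor could take the reference to clinical condition and algorithm as permission to score a correct decision not to prescribe as correct. A rule may also sit in the audit form, which is listed as Annex 7 but whose content is not in the text reviewed. This stands in part. The wording still asks for a prescription received, and if auditors may read it either way, the same record can be scored differently.

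Third, a denominator wider than indicator 29's is useful, because it can detect drugs that were indicated but not prescribed. That is correct, and it is why the denominator should not simply copy indicator 29's.

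Fourth, importance is easily overstated. A reader might infer that indicator 28 is the only check on use of the algorithm. It is not: indicator 29 counts prescriptions of drugs in the algorithm, and the audit under A.3.1 covers adherence to the guideline. A reader might also infer that clinicians are sent this percentage every two months. The plan promises regular feedback and gives two-monthly collection for indicators 27 and 28, but does not say that this figure is what is fed back.

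Finally, indicator 28 is broken down by cardiovascular risk level, which might partly expose a change in case mix. It is not broken down by drug treatment or drug indication, so the planned tables would not remove the effect.

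**Conclusion.** The point holds in conditional form. Numerator and denominator are mismatched as written. If a share q of audited patients has no drug indicated and is not credited, the indicator is capped at 1 − q and mixes prescribing quality with case mix.

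On the only available anchor, the ceiling lies between 93% and 100%. This assumes that audited CVRP records resemble the aware hypertensives of the 2016 population survey, and that those prescribed drugs in that survey all had an indication. The range is therefore a guide, not a bound. A larger drop caused by newly found patients starting more often without drugs is a tempting inference, but the documents give no figure for how such patients are treated.

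Severity is minor. This is a process indicator with no stated target. It does not enter the difference-in-difference analysis of the main outcomes or the sample size, and no effectiveness conclusion rests on it.

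**What to change.** In Table 4B, set the denominator of indicator 28 to audited records for which the defined algorithm indicates drug treatment. An indicated but absent prescription then counts as a failure, which preserves the advantage over indicator 29. Report separately, among the remaining audited records, the share correctly left without a drug, so that prescribing without an indication also stays visible.

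This is preferable to crediting non-prescription within a single ratio, which reaches 100% at full adherence but still depends on q. The change concerns counting only and takes no position on what the algorithm should contain.

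The cost is a change of wording and, if the audit form does not already record it, one yes/no item on whether a drug is indicated. The denominator will be slightly smaller. Since the algorithm has yet to be written, both can be settled together.
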